9.2 STUDY DOCUMENTATION

9.2.1 Investigator Information

Investigator information is included in the Study Procedures Manual, which is updated as needed.

9.2.2 Investigator Study Files

Documentation about the Investigator and Study staff, the IRB, and the institution is required before site initiation. Copies of these documents will be kept on-site in site-specific binders or electronic folders, along with the following supplemental information: a list of Investigator's obligations, the Investigator's Brochure, the Protocol and amendments, safety information, information about the IP, biological samples, and the laboratory, the Study Procedures Manual and study logs, electronic case report forms (eCRFs), records of monitoring activities, and correspondence between Sponsor or Study monitor and the Investigator.

Audit trails are generated automatically for eCRFs.

9.2.3 Case Report Forms and Source Documentation

The Investigator must make Study data accessible to the site monitor, other authorized representatives of the Sponsor, and the appropriate regulatory authority inspectors. The eCRF for each subject will be checked by the site monitor, and a final copy of the eCRF will be signed by the Investigator with an electronic signature. A copy of the final eCRFs will be provided to the Investigator after Study closure to be kept in the Investigator's Study files.

9.2.4 Retention of Study Documents

It is the Investigator's responsibility to retain Study essential documents for at least 2 years after the last approval of a marketing application in their country and until there are no pending or contemplated marketing applications in their country or at least 2 years have elapsed since the formal discontinuation of clinical development of the IP. These documents should be retained for a longer period if required by an agreement with the Sponsor. In such an instance, it is the responsibility of the Sponsor to inform the Investigator/institution as to when these documents no longer need to be retained.

9.3 CONFIDENTIALITY

Information about Study subjects will be kept confidential and managed according to the requirements of the Health Insurance Portability and Accountability Act of 1996 (HIPAA). Those regulations require a signed subject authorization informing the subject of the following:

- What protected health information (PHI) will be collected from subjects in the Study.
- Who will have access to that information and why.
- Who will use or disclose that information.
- The rights of a research subject to revoke their authorization for use of their PHI.

In the event that a subject revokes authorization to collect or use PHI, the Investigator, by regulation, retains the ability to use all information collected prior to the revocation of subject authorization. For subjects that have revoked authorization to collect or use PHI, attempts should be made to obtain permission to collect at least vital status (i.e., that the subject is alive) at the end of their scheduled Study period.

9.3.1 Data

The Investigator must keep all information confidential about the nature of the proposed investigation provided by the Sponsor or Study monitor to the Investigator (with the exception of information required by law or regulations to be disclosed to the IRB, the subject, or the appropriate regulatory authority).

9.3.2 Subject Anonymity

The anonymity of participating subjects must be maintained. Subjects will be identified by an assigned subject number on eCRFs and other documents retrieved from the site or sent to the Study monitor, Sponsor, regulatory agencies, central laboratories, or blinded reviewers. Documents that identify the subject (e.g., the signed informed consent form) must be maintained in strict confidence by the Investigator, except to the extent necessary to allow auditing by the appropriate regulatory authority, the Study monitor, or Sponsor representatives.

9.4 PROTOCOL COMPLIANCE

A protocol deviation is any noncompliance with the Protocol or Good Clinical Practice (GCP). Noncompliance may be on the part of the subject, the Investigator, or the Study site staff. As a result of major deviations as determined by the Study monitor, corrective actions are to be developed by the site and implemented promptly. Documentation of the deviation and corrective actions will be included in the data quality assessment during blinded review.

9.5 STUDY MONITOR FUNCTIONS AND RESPONSIBILITY

The Study monitor, in accordance with the Sponsor's requirements, will ensure that the Study is conducted and documented properly by carrying out the activities outlined in International Council for Harmonisation E6, Section 5.18.4.

9.5.1 Clinical Monitoring

The conduct of the Study will be closely monitored by representatives (Clinical Research Associates "CRAs" or study monitors) of the Sponsor, to verify adherence to the Protocol, ICH GCP guidelines, and applicable regulations. The CRA will verify eCRF entries by comparing them with hospital, clinical, office and/or Study records which will be made available for this purpose. CRAs will monitor the Study as outlined in the Monitoring Plan prepared for the Study.

During the Study, CRAs will contact the clinical site on a regular basis to assess and assure satisfactory enrollment rate, data recording, maintenance of required regulatory documentation, IP accountability, and compliance with the Protocol. The Investigator will ensure that all requested materials, including subject charts, eCRFs, source documents, laboratory records, and drug inventory records, will be available to the CRA if needed. At the end of the Study, a close-out visit will be performed.

Reports of all monitoring visits will be archived in the Trial Master File. The Investigator will allow the Sponsor's representatives, designee and/or any regulatory agency to have direct access to all Study records, eCRFs, corresponding subject medical records, IP dispensing records, and IP storage area, and any other documents considered source documentation. The Investigator also agrees to assist the representative, if required.

9.5.2 Quality Assurance, Auditing and Inspection

The Study is conducted under the sponsorship of VistaGen in compliance with the applicable international and local regulatory requirements as well as applicable ICH guidelines, Helsinki (1964, 1975, 1983, 1989 and 1996) and in respect of the VistaGen or its designee's SOPs for Study conduct and monitoring.

The Investigator will permit Study-related monitoring, audits, and inspections by the IRB, the Sponsor, and government regulatory bodies of all Study related documents (e.g., source documents, regulatory documents, data collection instruments, study data, etc.).

Participation as an Investigator in this Study implies acceptance of potential inspection by government regulatory authorities.

9.6 GENERAL INFORMATION

The Investigator should refer to the Investigator's Brochure, Study Procedures Manual, and any other information provided about this IP and details of the procedures to be followed during the Study.

9.7 PUBLICATION PLAN

Neither the partial, complete or any part of the results of the Study carried out under this protocol, nor any of the information provided by the Sponsor for the purposes of performing the Study, may be published or passed on by Investigator or any member of the Study site's staff to any third party without the prior written consent of VistaGen. Any Investigator involved with this Study is obligated to provide VistaGen with complete test results and all data derived from the Study in an efficient and timely manner. For multi-center studies, the first publication or disclosure shall be a complete, joint multi-center publication or disclosure.

APPENDIX A
SUBJECTIVE UNIT OF DISTRESS SCALE

[figure not shown]
Subjective Units of Distress Scale (SUDS) Thermometer

[figure not shown]
Using the Subjective Units of Distress Scale (also called the SUDS), you can record how anxious you feel in different situations by picking a number between 0 and 100; zero would mean totally relaxed or no anxiety and 100 is the most distress or anxiety imaginable.

[figure not shown]

APPENDIX D

LIEBOWITZ SOCIAL ANXIETY SCALE

[figure not shown]
Subject Initials	Subject #	Date	Visit #
		DD/MMM/YYYY	

[figure not shown]
Source Document: Protocol PH94B-CL026

[figure not shown]
Liebowitz Social Anxiety Scale (LSAS)

[figure not shown]
Item	Fear or Anxiety		Avoidance	
	Anxiety (S)	Anxiety (P)	Avoidance (S)	Avoidance (P)
1. Telephoning in public. (P)				
2. Participating in small groups. (P)				
3. Eating in public places. (P)				
4. Drinking with others in public places. (P)				
5. Talking to people in authority. (S)				
6. Acting, performing or giving a talk in front of an audience. (P)				
7. Going to a party. (S)				
8. Working while being observed. (P)				
9. Writing while being observed. (P)				
10. Calling someone you don't know very well. (S)				
11. Talking with people you don't know very well. (S)				
12. Meeting strangers. (S)				
13. Urinating in a public bathroom. (P)				
14. Entering a room when others are already seated. (P)				
15. Being the center of attention. (S)				
16. Speaking up at a meeting. (P)				
17. Taking a test. (P)				
18. Expressing a disagreement or disapproval to people you don't know very well. (S)				
19. Looking at people you don't know very well in the eyes. (S)				
20. Giving a report to a group. (P)				
21. Trying to pick up someone. (P)				
22. Returning good to a store. (S)				
23. Giving a party. (S)				
24. Resisting a high pressure sales person. (S)				
Total Performance (P) Subscore				
Total Social (S) Subscore				
Total Anxiety & Avoidance Subscore				
Total LSAS Score				

[figure not shown]
Rater Signature: _____ Initials: _____ Date: _____ / _____ / _____

[figure not shown]

[figure not shown]

[figure not shown]

APPENDIX G

HAMILTON DEPRESSION RATING SCALE

Subject Initials	Subject #	Date	Visit #
		DD/MMM/YYYY	

Source Document: Protocol PH94B-CL026

Hamilton Depression Rating Scale (HAM-D)

Check the appropriate response for each item according to how the subject has felt during the **past week**.

1. **DEPRESSED MOOD** (sadness, hopeless, helpless, worthless)

- 0 Absent.
- 1 These feeling states indicated only on questioning.
- 2 These feeling states spontaneously reported verbally.
- 3 Communicates feeling states non-verbally, i.e. through facial expression, posture, voice, tendency to weep.
- 4 Patient reports virtually only these feeling states in his/her spontaneous verbal and non-verbal communication.

2. **FEELINGS OF GUILT**

- 0 Absent.
- 1 Self-reproach, feels he/she has let people down.
- 2 Ideas of guilt or rumination over past errors or sinful deeds.
- 3 Present illness is a punishment. Delusions of guilt.
- 4 Hears accusatory or denunciatory voices and/or experiences threatening visual hallucinations.

3. **SUICIDE**

- 0 Absent.
- 1 Feels life is not worth living.
- 2 Wishes he/she were dead or any thoughts of possible death to self.
- 3 Ideas or gestures of suicide.
- 4 Attempts at suicide (any serious attempt rates 4).

4. **INSOMNIA – EARLY IN THE NIGHT**

- 0 No difficulty falling asleep.
- 1 Complains of occasional difficulty falling asleep, i.e. more than ½ hour.
- 2 Complains of nightly difficulty falling asleep.

5. **INSOMNIA – MIDDLE OF THE NIGHT**

- 0 No difficulty.
- 1 Patient complains of being restless and disturbed during the night.
- 2 Waking during the night - any getting out of bed rates 2 (except for purposes of voiding).

6. **INSOMNIA – EARLY HOURS OF THE MORNING**

- 0 No difficulty.
- 1 Waking in early hours of the morning but goes back to sleep.
- 2 Unable to fall asleep again if gets out of bed.

Rater Signature: _____ Initials: _____ Date: _____ / _____ / _____

Subject Initials	Subject #	Date	Visit #
		DD/MMM/YYYY	

Source Document: Protocol PH94B-CL026

Hamilton Depression Rating Scale (HAM-D)

Check the appropriate response for each item according to how the subject has felt during the **past week**.

7. WORK AND ACTIVITIES

- 0 No difficulty.
- 1 Thoughts and feelings of incapacity, fatigue or weakness related to activities, work, or hobbies.
- 2 Loss of interest in activity, hobbies or work - either directly reported by patient, or indirect listlessness, indecision and vacillation (feels he/she has to push self to work or activities).
- 3 Decrease in actual time spent in activities or decrease in productivity. Rate 3 if the patient does not spend at least three hours a day in activities (job or hobbies) excluding routine chores.
- 4 Stopped working because of present illness. Rate 4 if patient engages in no activities except routine chores, or if patient fails to complete routine chores unassisted.

8. RETARDATION (slowness of thought and speech, impaired ability to concentrate, decreased motor activity)

- 0 Normal speech and thought.
- 1 Slight retardation during the interview.
- 2 Obvious retardation during the interview.
- 3 Interview difficult.
- 4 Complete stupor.

9. AGITATION

- 0 None.
- 1 Fidgetiness.
- 2 Playing with hands, hair, etc.
- 3 Moving about, can't sit still.
- 4 Hand wringing, nail-biting, hair pulling, biting of lips.

10. ANXIETY PSYCHIC

- 0 No difficulty.
- 1 Subjective tension and irritability.
- 2 Worrying about minor matters.
- 3 Apprehensive attitude apparent in face or speech.
- 4 Fears expressed without questioning.

Rater Signature: _____ Initials: _____ Date: _____ / _____ / _____

Subject Initials	Subject #	Date	Visit #
		DD/MMM/YYYY	

Source Document: Protocol PH94B-CL026

Hamilton Depression Rating Scale (HAM-D)

Check the appropriate response for each item according to how the subject has felt during the **past week**.

11. ANXIETY SOMATIC (Physiological concomitants of anxiety), such as:

Gastrointestinal - dry mouth, wind, indigestion, diarrhea, stomach cramps, belching
 Cardiovascular - palpitations, headaches
 Respiratory - hyperventilation, sighing, sweating
 Urinary frequency
 Sweating

0 Absent.
 1 Mild.
 2 Moderate.
 3 Severe.
 4 Incapacitating.

12. SOMATIC SYMPTOMS GASTROINTESTINAL

0 None.
 1 Loss of appetite but eating without encouragement. Heavy feelings in abdomen.
 2 Difficulty eating without urging. Requires laxatives or medication for bowels or medication for gastrointestinal symptoms.

13. GENERAL SOMATIC SYMPTOMS

0 None.
 1 Heaviness in limbs, back or head. Backaches, headaches, muscle aches. Loss of energy and fatigability.
 2 Any clear-cut symptom rates 2.

14. GENITAL SYMPTOMS (symptoms such as loss of libido, menstrual disturbances)

0 Absent.
 1 Mild.
 2 Severe.

15. HYPOCHONDRIASIS

0 Not present.
 1 Self-absorption (bodily).
 2 Preoccupation with health.
 3 Frequent complaints, requests for help, etc.
 4 Hypochondriacal delusions.

16. LOSS OF WEIGHT (according to the patient)

0 No weight loss.
 1 Probable weight loss associated with present illness.
 2 Definite (according to patient) weight loss.
 3 Not assessed.

Rater Signature: _____ Initials: _____ Date: _____ / _____ / _____

Subject Initials	Subject #	Date	Visit #
		DD/MMM/YYYY	

Source Document: Protocol PH94B-CL026

Hamilton Depression Rating Scale (HAM-D)

Check the appropriate response for each item according to how the subject has felt during the **past week**.

17. **INSIGHT**

- 0 Acknowledges being depressed and ill.
- 1 Acknowledges illness but attributes cause to bad food, climate, overwork, virus, need for rest, etc.
- 2 Denies being ill at all.

Total (17 Items):

Rater Signature: _____ Initials: _____ Date: _____ / _____ / _____

APPENDIX H

CLINICAL GLOBAL IMPRESSION IMPROVEMENT SCALE

Subject Initials	Subject #	Date	Visit #
		DD/MMM/YYYY	

Source Document: Protocol PH94B-CL026

Clinical Global Impression (CGI) Improvement Scale

	[REDACTED]

Rater Signature: _____ Initials: _____ Date: ____ / ____ / ____

8.6	Hamilton Depression Scale (HAM-D)	30
9	References.....	31
10	[REDACTED]	

LIST OF ABBREVIATIONS

AE	Adverse Event
ANCOVA	Analysis of Covariance
C-SSRS	Columbia Suicidality Severity Rating Scale
CGI-I	Clinical Global Impression Scale of Improvement
CS	Clinically Significant
CSR	Clinical Study Report
eCRF	Electronic Case Report Form
ECG	Electrocardiogram
GCP	Good Clinical Practice
i.n.	Intranasal
ICE	Intercurrent Event
ICF	Informed Consent Form
IP	Investigational Product
IRB	Institutional Review Board
ITT	Intent to Treat
LLN	Lower Limit of Normal
LSAS	Liebowitz Social Anxiety Scale
MedDRA	Medical Dictionary for Medical Affairs
MINI	Mini International Neuropsychiatric Interview
n	Sample Size
N	Population Size
NCS	Not Clinically Significant
PCS	Potentially Clinically Significant
PGI-C	Patient Global Impression of Change
PH94B	PH94B Nasal Spray
PT	Preferred Term
Q1	First Quartile
Q3	Third Quartile
QTcF	QT Corrected with Fridericia Formula
SAD	Social Anxiety Disorder
SAE	Serious Adverse Event
SD	Standard Deviation
SI	International System
SOC	System Organ Class
SUDS	Subjective Units of Distress Scale
TEAE	Treatment-Emergent Adverse Event
UDS	Urine Drug Screen
ULN	Upper Limit of Normal
VistaGen	VistaGen Therapeutics, Inc.
WHO	World Health Organization
WHO DD	WHO Drug Dictionary

1 INTRODUCTION

The statistical analysis plan (SAP) details the planned statistical analysis methods required to address the study objectives as described in PH94B-CL026: A Phase 3 Multicenter, Randomized, Double-blind, Placebo-controlled Clinical Trial of PH94B Nasal Spray for the Acute Treatment of Anxiety Induced by a Public Speaking Challenge in Adult Subjects with Social Anxiety Disorder (PALISADE-1).

This SAP should be read in conjunction with the study protocol and case report form (CRF). The version of this SAP is based on the protocol PH94B-CL026 version 2.0 dated 03-Jan-2022 and the CRF dated 23-Dec-2021. Changes to these documents may result in subsequent changes to the SAP. The final, sponsor-approved version of the SAP must occur prior to database lock. Analysis programming activities will initiate upon SAP approval.

1.1 Modification History

SAP Revision Chronology:	Date:	Details:
v1.0 to v2.0	09-May-2022	[REDACTED]

1.2 Changes to the Planned Analysis

There are no changes to the planned analysis from the Protocol. Any deviations from the original statistical analysis plan will be described and justified in the final clinical study report.

2 STUDY OBJECTIVES AND ENDPOINTS

Objectives	Endpoints
Efficacy	
Primary	
To evaluate whether the efficacy of PH94B to relieve acute anxiety induced during a public speaking challenge in adult subjects with SAD is greater than that for placebo as measured by the Subjective Units of Distress Scale (SUDS).	The difference in average SUDS score during a 5-minute public speaking challenge after treatment with PH94B or placebo at Visit 3 (Treatment) and the average SUDS score during a similar 5-minute public speaking challenge after treatment with placebo at Visit 2 (Baseline).
Secondary	
The comparison of PH94B-treated subjects with placebo-treated subject with regard to clinician-observed change in subject's response to an anxiety-provoking situation between Visit 2 and Visit 3 as measured by Clinical Global Impression Scale of Improvement (CGI-I).	The proportion of Clinical Global Impression Scale of Improvement (CGI-I) scores of 1 [REDACTED] or 2 [REDACTED] [REDACTED] recorded at the end of Visit 3.
[REDACTED]	[REDACTED]
Safety	
The determination of safety and tolerability of PH94B compared to placebo in adult subjects with SAD.	
• AEs, suicidal ideation (C-SSRS), and level of depression (HAM-D)

Objectives	Endpoints
	
• Changes from Screening in laboratory parameters, vital signs, ECGs, and physical examinations.

3 STUDY DESIGN

3.1 General Description

The Study is a Phase 3, multicenter, randomized, double-blind, placebo-controlled, parallel design group trial of the efficacy and safety of PH94B in the acute treatment of anxiety in adult subjects diagnosed with SAD as defined by the Diagnostic and Statistical Manual of Mental Disorders, 5th Edition and confirmed by the Mini International Neuropsychiatric Interview (MINI).

Subject participation in the study will last a total of 3 to 7 weeks, depending on the duration of the screening period and intervals between visits. Upon signing an informed consent, all subjects will complete Visit 1 (Screening) and enter a screening period [REDACTED]. If subjects meet all eligibility criteria at the end of the screening period, subjects will complete Visit 2 (Baseline) and participate in a 5-minute public speaking challenge [REDACTED]

[REDACTED]. At Visit 3 (Treatment), the subject will be randomized. The subject will self-administer randomized investigational product (IP) and will then undergo a 5-minute public speaking challenge with SUDS scores being collected [REDACTED] by the same trained observer who was present for that subject during the Visit 2 public speaking challenge. At the end of the Visit 3 public speaking challenge, the subject will complete the [REDACTED], and the site personnel will complete the Clinical Global Impression Scale of Improvement (CGI-I) assessment. One week (\pm 2 days) after the completion of Visit 3, subject will come back for Visit 4 (Follow-up) that will involve a repeat of the safety psychiatric assessments conducted at Screening [REDACTED]

3.2 Study Population

Eligibility for participation in the study will be determined from demographic information, medical and psychiatric history, physical and psychiatric examination, electrocardiogram (ECG), clinical laboratory findings, and clinical rating scale assessments performed at the Screening Visit. Subjects may be recruited from the Investigator or sub-Investigator clinical practices, center's existing database, referring physicians, or direct advertisement or other lead generation source.

3.3 Randomization and Blinding

Randomization will be stratified within study site with a ratio of 1:1.

[figure not shown]
Each study site will be provided with a supply of blinded IP, each vial individually numbered with a unique alpha-numeric identification code. For Visit 2 and Visit 3, the interactive system

will provide a unique vial identification code indicating the medication vial to be dispensed to the subject. The vial identification codes will be recorded in the drug dispensing record and the electronic case report form (eCRF).

The vial number can be used to break the blind if deemed medically necessary by the medical monitor. Contact information will be provided to the study site.

3.4 Sample Size

Sample size considerations are based on the similarly designed Phase 2 randomized, double-blind, placebo-controlled clinical study of PH94B with the primary outcome variable being average subjective anxiety based on the SUDS scores.

4 ANALYSIS POPULATIONS

4.1 All Subjects Population

All Subjects Population: The All Subjects Population will include all subjects who sign an informed consent, have a Screening Visit performed, and are entered into the eCRF for the study. The All Subjects Population will be used for summaries of subject disposition and protocol deviations.

4.2 Intent-to-Treat Population

Intent-to-Treat (ITT) Population: The ITT Population will include all subjects who are randomized. Subjects in this population will be analyzed according to the randomized treatment assignment, regardless of treatment received.

4.3 Safety Population

Safety Population: The Safety Population will include all subjects who receive IP. AEs will be classified by time of occurrence and Visit 3 group assignment to identify more clearly those arising after exposure to [REDACTED] only and those arising after exposure to [REDACTED]. Subjects will be analyzed according to the treatment received, regardless of the randomized treatment assignment.

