5.2.2 Visit 2 (Baseline)

For subjects continuing to meet all eligibility criteria, the following Visit 2 assessments will be completed:

- Measure vital signs after the subject has rested for 5 minutes: seated systolic and diastolic blood pressure, heart rate, respiratory rate, and body temperature.
- Obtain urine sample for Urine Drug Screen: Instant Exam to be performed on site, with results thoroughly documented in the source; urine sample to be sent to central laboratory for confirmation if on-site UDS is positive [REDACTED]
[REDACTED].

- For females of child-bearing potential, obtain urine sample and complete on-site urine pregnancy test.
- Record concomitant medication use including the completion of any washout.
- Review all inclusion and exclusion criteria.

For subjects meeting all study inclusion criteria and no study exclusion criteria, the following Visit 2 procedures will be performed:

[figure not shown]
- Introduce the self-rated anxiety scale, the Subjective Units of Distress Scale (SUDS), to the subject and review the descriptions of the various SUDS scores (Appendix A).
- [REDACTED]
- Dispense and instruct subject to self-administer IP [REDACTED]
[REDACTED]
- The subject will be returned to a waiting area after IP dosing.
- [REDACTED] the subject will be informed that they must give a 5-minute speech to a live audience of [REDACTED]
[REDACTED]
- [REDACTED]
[REDACTED]
[REDACTED]
- The subject will be given 3 minutes to organize their thoughts on their upcoming speech.
- The subject will be escorted into a room to give a 5-minute speech in front of three neutral observers after the last SUDS anticipatory anxiety score is collected
[REDACTED]
[REDACTED]
[REDACTED]
[REDACTED]

- [REDACTED]

[REDACTED], the subject will be given information on attending the next visit (Visit 3), else the subject will complete the remaining assessments for Visit 2, will not be randomized, and will be discharged from the study [REDACTED]

- If the subject cannot complete the speech due to anxiety levels, the SUDS level will be requested from them before they leave the room and all remaining time points will be marked as not done.
- Record any AEs reported.
- [REDACTED]

For the subject attending the next visit (Visit 3), it will be scheduled 1 week (\pm 2 days) after the date of Visit 2.

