5.2 Reference Dates and Definitions

The reference dates for this study are as follows:

- Informed consent date is defined as the eCRF-provided date on which a subject signed the informed consent form.
- Randomization date is defined as the date on which the subject is randomized to study treatment.
- Treatment start date is defined as the date of first dose of IP including dosing of [REDACTED] at Visit 2.

- Treatment end date is defined as the date of last dose of IP.
- The calculation of age will use the informed consent date as its reference date.
- Safety Population data, such as AEs and laboratory assessments, will use the treatment start date as a reference date. In this study, because first dose of PH94B will not occur until Visit 3, AEs will be reported for both prior to Visit 3 IP administration and post.
- Study day will be based on treatment start date as a reference date.

Variable	Definition
Baseline Value	Baseline may refer to the last non-missing value [REDACTED]
Post-Baseline Value	Defined as values collected after IP administration.
Change from Baseline	Defined as: Post-Baseline Value – Baseline Value
Percent Change from Baseline	Defined as: (Value at Post-baseline Visit – Value at Baseline)/Value at Baseline x 100. Note: To compute percent change from baseline, the baseline value cannot be equal to zero.
Temperature (in °C)	= (temperature (in °F) - 32) * 5/9
Height (in cm)	= height (in inches) * 2.54
Weight (in kg)	= weight (in lbs) * 0.4536

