6.2 Protocol Deviations

Protocol deviations will be identified via the eCRFs and classified as major or minor deviations before the database is locked. Protocol deviations will be summarized for the All Subjects Population by treatment group (including “not randomized”) and overall. Data will also be presented in a by-subject listing.

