7.1.2 Primary Endpoint and Analysis – Average SUDS Scores

The primary efficacy endpoint of the study is the difference in average SUDS score during a 5-minute public speaking challenge after treatment with PH94B or placebo at Visit 3 and the average SUDS score during a similar 5-minute public speaking challenge after treatment with placebo at Baseline (Visit 2).

The SUDS, used at Visit 2 and Visit 3 as part of each public speaking challenge, is scored 0–100. It is a standard instrument for rating social and performance anxiety in patients with SAD during role playing situations. Appendices A and B in the study protocol provide further detail on the public speaking challenge and SUDS scores.

An ANCOVA model will be used to test the null hypothesis that there is no difference in change from baseline average SUDS scores between PH94B- and placebo-treated subjects. Treatment group and analysis site will be included as factors and baseline average SUDS score as a covariate. [REDACTED]

[REDACTED]

[REDACTED]

[REDACTED]

It is expected that all subjects who are randomized at Visit 3 will complete the Visit 3 public speaking challenge immediately after randomization and be included in the primary efficacy analysis. [REDACTED]

[REDACTED]

The effects of the missing data will be evaluated through the results of the planned sensitivity analyses described in Section 6.2.1.3.

7.1.2.1 *Sensitivity Analyses*

Sensitivity analyses will be performed for the primary efficacy outcome. If imputation of missing data is required, a complete case sensitivity analysis will be implemented.

Additional sensitivity analyses may include imputation using treatment group mean SUDS change scores and imputation of zero change from baseline.

In order to satisfy requirements of a CAPA, an additional sensitivity analysis will be done by performing the primary analysis with Subjects 0101, 0103, and 0104 removed. If removal of these subjects results in an analysis site with too few patients for parameter estimation, then the model will be run without analysis site, both with and without the three subjects.

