8.1 Adverse Events

An AE is any symptom, sign, illness, or experience that develops or worsens in intensity during the course of the study. Any newly developed illnesses or injuries should be regarded as adverse events. AEs will be assessed for severity, relationship to study drug, and seriousness. Further details about AE determination and categorization can be found in the study protocol.

Serious adverse events (SAEs) will be recorded starting at Visit 1 after signing informed consent. AEs will be recorded from the time of first IP administration through end of study. A TEAE is defined as any AE occurring on or after start of IP. All summaries of AEs will be based on TEAEs. All AEs recorded on the eCRF, whether treatment-emergent or not, will be presented in a data listing. Non-TEAEs will be flagged in the listings.

All AE data will be reported for two time periods: prior to Visit 3 dosing, and during or after Visit 3 dosing. This is due to the fact that all subjects receive [REDACTED] at Visit 2 and then receive randomized treatment [REDACTED] at Visit 3. AEs will be assigned to a time period based on AE start date. An AE that starts on the day of Visit 3 dosing will be assigned as “during or after Visit 3 dosing”. From Screening until IP administration at Visit 2, any clinically significant abnormality should be recorded as a preexisting condition in the medical history, not as an AE.

All AE terms will be coded by using MedDRA, version 24.0 – Mar 2021.

Missing and partially missing start and/or end dates will be imputed for the purpose of determining treatment-emergent flags and AE categorization, according to Section 5.7.

The incidence of TEAEs will be summarized by maximum severity and strongest relationship to IP. When calculating the incidence of TEAEs, each TEAE will be counted only once for a given subject within a MedDRA category (i.e., overall, SOC, or PT). When TEAEs are summarized within levels of another TEAE assessment (i.e., severity or relationship), TEAEs will be counted once per subject at the worst level of the assessment (i.e., greatest severity or relationship to IP). Any missing severity assessments will be assumed to be severe and missing relationship assessments will be assumed to be related.

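### Does the Safety Population rule put never-randomised subjects dosed only at Visit 2 into the placebo arm and dilute its adverse event rates?

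*SAP*

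**What the plan says.** SAP 4.3 sets membership by dosing alone: "The Safety Population will include all subjects who receive IP". The Visit 2 dose counts as IP, because SAP 5.2 reads "Treatment start date is defined as the date of first dose of IP including dosing of" a product whose name is blacked out, given at Visit 2. SAP Sections 2 and 7.1.2 identify that product as placebo. Protocol 5.2.2 provides that some subjects, after the Visit 2 dose and speech, "will not be randomized, and will be discharged from the study".

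Four rules bear on where these subjects appear in the safety tables:

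- SAP 4.3, on events: "AEs will be classified by time of occurrence and Visit 3 group assignment".
- SAP 4.3, on subjects: "Subjects will be analyzed according to the treatment received, regardless of the randomized treatment assignment".
- SAP 5.1: tables are in general laid out by Visit 3 treatment, with columns PH94B, Placebo and Overall.
- SAP 8.1: "All AE data will be reported for two time periods: prior to Visit 3 dosing, and during or after Visit 3 dosing".

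For deviations only, the SAP names a further column. Section 6.2 says "Protocol deviations will be summarized for the All Subjects Population by treatment group" and includes a group for subjects who were not randomised. The safety section names no such group.

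**The concern.** A subject dosed only at Visit 2 has received nothing but placebo. If the as-treated sentence in SAP 4.3 is taken in isolation, and actual treatment is read from the batch ID as SAP 5.5 provides, a programmer might label that subject Placebo. Such a subject has no Visit 3 dose and so cannot have an event in the later period. Each one would add to the placebo denominator and nothing to the numerator. Placebo rates would fall, PH94B would look worse by comparison, and the Safety Population baseline tables would set a randomised arm against randomised subjects plus rejected ones.

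Comparing safety with placebo is a stated objective, and descriptive rates are its only output, so a distorted denominator would matter. The explicit group in Section 6.2 shows that the authors had non-randomised subjects in mind, which makes the silence in Section 8 more noticeable.

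**Working it through.** **Inputs.** Planned randomised: 208, as 104 per arm (Protocol synopsis); 2 × 104 = 208 agrees. Planned screened: up to 470 (same place). The assumptions behind 208 are blacked out, so it cannot be re-derived, but nothing here depends on power. The documents give no number of Visit 2-only subjects, no expected adverse event rate and no safety denominator.

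**Upper limit.** 470 − 208 = 262 not randomised. This includes everyone who fails screening before any dose, so the Visit 2-only number m lies somewhere below it. I assume 10%, 20% and 40% of 262, that is m = 26, 52 and 105, and a true rate of 10% after Visit 3.

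**Formulas.** Placebo rate displayed if all m are added to that column: 10% × 104/(104 + m). Overall rate displayed if they are added only there: 10% × 208/(208 + m).

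| m (assumed) | Placebo N | Placebo rate shown | Overall N | Overall rate shown |
|---|---|---|---|---|
| 0 | 104 | 10.0% | 208 | 10.0% |
| 26 | 130 | 8.0% | 234 | 8.9% |
| 52 | 156 | 6.7% | 260 | 8.0% |
| 105 | 209 | 5.0% | 313 | 6.6% |
| 262 (extreme bound) | 366 | 2.8% | 470 | 4.4% |

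In the placebo case, the PH94B-to-placebo ratio would be inflated by (104 + m)/104: 1.25, 1.50, 2.01 and 3.52 for the four non-zero rows.

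**Which rows apply?** That depends on the text.

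1. SAP 4.3 sorts adverse events by time and by Visit 3 group, in the sentence just before the as-treated one. A subject never randomised has no Visit 3 group.
2. SAP 5.1 bases the table columns, and the summaries of continuous and categorical data, on Visit 3 treatment. SAP 8.2 (laboratory shifts), 8.5 (C-SSRS) and 8.6 (HAM-D) repeat this.
3. SAP 5.5 introduces assigned and actual treatment in the setting of random assignment at Visit 3. The as-treated sentence sets treatment received against randomised assignment. That is the usual rule for a randomised subject who was given the wrong vial, and it presupposes an assignment that these subjects lack.
4. For laboratory and ECG summaries, SAP 5.1 uses non-missing values. Subjects with no later measurement drop out of change and shift tables whatever column they sit in.
5. SAP 8.1 separates events before Visit 3 dosing from those during or after it, so events after the lead-in dose cannot enter the later counts.

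Under this reading the placebo denominator stays at about 104 and the dilution factor is 104/104 = 1.00. The placebo columns of the table do not arise. The Overall columns remain possible only if the whole Safety Population is used as the denominator after Visit 3.

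**The case for a change.** The best case for a change is that no sentence says outright which rule governs these subjects. SAP 5.1 is qualified as applying in general, SAP 5.5 does not say whether the batch is that of the Visit 2 or the Visit 3 vial, and none of the three named columns fits a subject without a Visit 3 group. The non-missing rule does not settle adverse event incidence either, since a subject without an event is not a missing value. Two teams could in principle produce different tables, and one sentence would prevent it.

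Part of this stands. Visit 2-only subjects are in the Safety Population, and the visible text gives neither a column for them nor a denominator for the later period. What does not stand is the step from there to a diluted placebo arm. It takes one sentence of SAP 4.3 without its neighbour and applies a wrong-vial rule to people who were never assigned. Two further cautions apply. The words in SAP 4.3 that describe the exposure groups are blacked out, as is text around the discharge rule in Protocol 5.2.2, so silence in the visible text is weak evidence of an omission. The table shells are also not among the documents.

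**Conclusion.** The plan does not place never-randomised subjects in the placebo arm. On its Visit 3 grouping, the effect on the PH94B-to-placebo safety comparison is zero. This rests on reading the as-treated sentence together with the rest of SAP 4.3 and with SAP 5.1 and 5.5, which is the natural reading.

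The residual gap is the Overall column after Visit 3. If the full Safety Population were its denominator, an assumed 10% rate would be displayed as 8.9% to 6.6% for 26 to 105 assumed Visit 2-only subjects; the documents do not allow the true number to be fixed. No comparison rests on that column. SAP Section 8 plans no formal safety testing, all adverse events are listed by subject, and the efficacy analyses use the ITT set, so neither type I error nor power is touched. An analyst who follows the Visit 3 grouping will use subjects dosed at Visit 3 for the later period without being told to. This is missing detail that is filled sensibly in programming, and it does not require an amendment.
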